2.3. Benefit/Risk Assessment

More detailed information about the known and expected benefits and risks and reasonably expected adverse events (AEs) of efgartigimod may be found in the IBs for efgartigimod⁴ and rHuPH20⁵.

2.3.1. Efgartigimod Risk Assessment

Overall, efgartigimod IV has been well tolerated in healthy participants subjects as well as in patients with gMG. Efgartigimod PH20 SC was well tolerated in healthy participants. No major safety findings have arisen in ongoing and completed studies with either formulation of efgartigimod. Further information can be found in the IB⁴.

Potential Risk of Clinical Significance	Summary of Data/Rationale for Risk	Mitigation Strategy
	Study Intervention (s)	
Immune modulation leading to increased infection risk	Efgartigimod reduces IgG levels, potentially hindering immune response and increasing the infection risk. However, no opportunistic infection with efgartigimod has been observed. Efgartigimod treatment may be associated with a small increase in the frequency of infections. However, the type and severity of these infections are not different to those which patients with gMG are ordinarily susceptible. There is no increase in the type of infectious events that might be expected from high degrees of immunosuppression	Participants with clinically significant uncontrolled infections, malignancies, recent surgeries, and/or the presence of certain viral infections are excluded (see Section 5.2). Administration of efgartigimod to a participant will be interrupted if a clinically significant infection occurs. Infections are considered an adverse event of special interest (AESI) and a detailed questionnaire will be completed for any infectious events.

Potential Risk of Clinical Significance	Summary of Data/Rationale for Risk	Mitigation Strategy
	Study Intervention (s)	
	(eg, tuberculosis or opportunistic infections).	
Injection and/or infusion-related reactions (IRRs)	All therapeutic proteins have the potential to elicit antibody or other immune or nonimmune mediated responses, potentially resulting in hypersensitivity or allergic reactions such as rash, urticaria, angioedema, serum sickness, and anaphylactoid or anaphylactic reactions. None of the participants treated	Participants will be monitored at the site for 1 hour after administration and administration site reactions will be monitored continuously (see Section 1.3).
	with either efgartigimod formulation had a treatment- emergent adverse event (TEAE) that was a drug hypersensitivity or anaphylactic reaction	
Potential risk to teratogenicity/fetotoxicity	No clinical studies have been performed to evaluate reproductive risks. However, nonclinical studies performed suggest that there is no risk of teratogenicity or fetotoxicity.	Pregnant women are excluded. Participants who are women of childbearing potential (WOCBP) must use a highly effective or acceptable method of contraception (see inclusion criterion 8 and Section 10.5)

2.3.2. Efgartigimod Benefit Assessment

Efgartigimod has been shown to effectively reduce IgG antibodies in several clinical studies, including in healthy subjects, patients with immune thrombocytopenia (ITP), patients with pemphigus vulgaris, and patients with gMG (see the IB). Patients with gMG also saw improvements in gMG symptoms and quality of life. Studies involving patients with gMG are described in the following text.

- A phase 2 study (ARGX-113-1602) enrolled patients with gMG that were seropositive for AChR binding autoantibodies (AChR-Ab) and had an MG-ADL total score of ≥5 with more than 50% of this score attributed to nonocular items. Participants received efgartigimod IV 10 mg/kg or placebo q7d for 4 infusions.
 - Efgartigimod IV showed statistically significant improvements as compared to placebo in clinical evaluations of MG symptoms, including the MG-ADL and the QMG.
 - The efgartigimod IV treatment arm showed a substantial percent reduction from baseline in total IgG levels as compared to the placebo arm, where no discernable difference from baseline was observed.

- Efgartigimod IV was safe and well tolerated, with all treatment-emergent adverse events (TEAEs) classified as mild or moderate.
- A phase 3 study (ARGX-113-1704) enrolled patients with gMG with an MG-ADL total score ≥5 with more than 50% of the total score coming from nonocular symptoms, regardless of AChR-Ab presence in the serum. Participants received efgartigimod IV 10 mg/kg or placebo q7d for 4 infusions, with additional treatment cycles allowed based on the clinical response of the participant as evaluated by the MG-ADL total score.
 - The efgartigimod IV treatment arm had a statistically significantly higher percentage (67.7%) of MG-ADL responders as compared to the placebo arm (29.7%) among AChR-Ab positive patients. In the overall population (AChR-Ab positive and AChR-Ab negative participants), the efgartigimod treatment arm also reported a significantly higher percentage of MG-ADL responders (67.9%) compared to the placebo arm (37.3%).
 - The efgartigimod IV treatment arm had a statistically significantly higher percentage of QMG responders (63.1%) as compared to the placebo arm (14.1%) among AChR-Ab positive participants.
 - In the AChR-Ab seropositive population, the maximum mean percent change from baseline in total IgG levels was approximately 61% 1 week after the last infusion of a treatment cycle. No substantial mean percent change in total IgG levels from baseline was observed in the placebo arm. The results were comparable between AChR-Ab seropositive participants and the overall population.
 - Efgartigimod IV 10 mg/kg q7d was safe and well tolerated. The efgartigimod IV arm had a lower percentage of participants reporting TEAEs than the placebo arm. The majority of TEAEs reported were mild or moderate in severity.

2.3.3. rHuPH20 Risk Assessment

More information on the use of rHuPH20 (brand name Hylenex) is available in the rHuPH20 IB^5 .

SC injections were well tolerated in healthy subjects, dehydrated pediatric patients, hospice and palliative care patients, patients with type 1 and 2 diabetes, and patients with rheumatoid arthritis. SC injections of rHuPH20 alone or in combination with lactated Ringer's solution, normal saline, co-injected drugs (eg, morphine, ceftriaxone, ondansetron), peptides (eg, insulin and insulin analogs), or proteins (IgG and adalimumab) have been well tolerated in all clinical studies.

Most AEs observed were mild, transient injection site reactions, including erythema, pain, bruising, pruritus, burning, tenderness, edema, induration, irritation, paresthesia, numbness, and rash. Moderate injection site reactions, which occurred less frequently, include burning, erythema, pain, and numbness. Mild-to-moderate headache was also reported.

Hylenex prescribing information as of February 2016 contains the following warnings and precautions:

- rHuPH20 should not be injected into or around an infected or acutely inflamed area because of the danger of spreading a localized infection. rHuPH20 should not be used to reduce the swelling of bites or stings.
- rHuPH20 should not be applied directly to the cornea. It is not for topical use.

2.3.4. rHuPH20 Benefit Assessment

rHuPH20 locally degrades hyaluronan under physiological conditions, acting as a permeation enhancer in the SC space. rHuPH20 activity allows for increased dispersion and absorption of coadministered therapies and facilitates the delivery of larger volumes in rapid SC injections with limited swelling, induration, or pain. rHuPH20 may enhance the dispersion and absorption of efgartigimod, allowing an SC injection to achieve the target exposure, PD effect, and associated clinical benefit. This formulation and SC administration are expected to improve patient convenience as compared to the IV formulation, as participants or their caregivers will be permitted to administer efgartigimod PH20 SC once they are competent to do so.

2.3.5. Overall Benefit/Risk Conclusion

Taking into account the measures taken to minimize risk to study participants, the potential risks identified in association with efgartigimod and rHuPH20 are justified by the anticipated benefits that may be afforded to participants with gMG.

3. OBJECTIVES AND ENDPOINTS

Objectives	Endpoints
Primary	
• To demonstrate that the PD effect of injections of 1000 mg efgartigimod PH20 SC, administered once per week (q7d) for 4 administrations, is noninferior to that of IV infusions of efgartigimod at a dose of 10 mg/kg administered q7d for 4 administrations.	• Percent reduction from baseline in total IgG levels at day 29, ie, 7 days after the fourth IV or SC administration
Secondary	
• To compare the PD effect of efgartigimod PH20 SC and efgartigimod IV over time	• Absolute values, change from baseline and percent reduction from baseline in total immunoglobulin (IgG) levels over time
	• Absolute values, change from baseline and percent reduction from baseline in AChR-Ab levels over time in AChR- Ab positive patients
	• Absolute values, change from baseline, and percent reduction from baseline in IgG subtype levels (IgG1, IgG2, IgG3, and IgG4) over time
	• Area under the effect curve (AUEC) of the percentage reduction from baseline total IgG and similar AUEC for each IgG subtype per dosing interval (days 1–8, days 8–15, days 15–22, and days 22–29), days 1–29, and over the entire study (days 1–71)
• To evaluate the PK of efgartigimod PH20 SC and efgartigimod IV	• PK parameters: maximum concentration (C _{max}) (after all doses for the IV treatment arm), concentration observed predose (C _{trough})

Objectives	Endpoints
• To evaluate the safety, tolerability, and immunogenicity of efgartigimod PH20 SC and efgartigimod IV	 Incidence and prevalence of anti-drug antibodies (ADAs) against efgartigimod Incidence and prevalence of ADAs against rHuPH20 in the SC treatment arm Incidence and severity of adverse events (AEs), incidence of serious adverse events (SAEs), and changes in laboratory test results, physical examination results, vital signs, and electrocardiogram (ECG) results
• To evaluate the clinical efficacy of efgartigimod PH20 SC and efgartigimod IV	 Number and percentage of Myasthenia Gravis Activities of Daily Living (MG- ADL) responders Numbers and percentage of QMG responders Change from baseline in MG-ADL total score over time Change from baseline in QMG score over time
Exploratory	

4. **STUDY DESIGN**

4.1. **Overall Design**

- This is a phase 3, multicenter, randomized, open-label, parallel-group study to evaluate the noninferiority of the PD effect of efgartigimod PH20 SC 1000 mg as compared to efgartigimod IV 10 mg/kg in patients with gMG. The safety, clinical efficacy, immunogenicity, PK of efgartigimod PH20 SC 1000 mg and efgartigimod IV 10 mg/kg will also be assessed.
- The total study duration is approximately 12 weeks:
 - approximately 2 weeks of screening, with an additional 5 days allowed as needed to ensure AChR-Ab test results have been received
 - 3 weeks of treatment
 - o 7 weeks of follow-up
- The primary target population is adult patients with generalized myasthenia gravis (gMG), who have an MG-ADL total score ≥5 points and greater than 50% of the total score attributed to nonocular symptoms, at screening and baseline. Participants must be receiving a stable dose of concomitant treatment for gMG.
- Serum from participants will be tested to determine their AChR-Ab status. Up to 20% of the participants randomized can be seronegative for AChR-Abs in both the overall population and the Japanese participant population.
- Randomization will be stratified by Japanese versus non-Japanese participants. Within non-Japanese participants, randomization will be further stratified by AChR-Ab status.
- After confirmation of eligibility, participants will be randomized 1:1 at the day 1 visit to receive efgartigimod IV 10 mg/kg or efgartigimod PH20 SC 1000 mg every 7 days (q7d) for 4 administrations.
- Efgartigimod IV will be administered by a 1-hour IV infusion performed by the site staff.
- Efgartigimod PH20 SC will be administered by injection into the abdominal subcutaneous tissue. Participants receiving efgartigimod PH20 SC or their caregivers will be trained in self-administration or caregiver-supported administration of the IMP. If the participant or the caregiver successfully completes the training to the satisfaction of the investigator and the participant, the participant or the caregiver may administer the second, third and/or fourth injections at the site under supervision.
- At End of Study (EoS), eligible participants will be offered the option to roll over into a single-arm extension study ARGX-113-2002 to receive efgartigimod PH20 SC. Participants who complete this study may be eligible to participate in the extension study.

4.2. Scientific Rationale for Study Design

The aim of this study is to assess the PD, PK, safety, tolerability, immunogenicity, and clinical efficacy of efgartigimod coadministered with rHuPH20 subcutaneously (efgartigimod PH20 SC) as compared to efgartigimod IV in patients with gMG. IgG autoantibodies lead to gMG

Clinical Study Protocol ARGX-113-2001 v2.0 Efgartigimod IV and SC

symptoms, resulting from destruction of important molecules in the NMJ, including AChR. IgG antibody total levels, levels of IgG subtypes (IgG1, IgG2, IgG3, and IgG4), and levels of AChR-Abs will be evaluated as an objective surrogate measure for gMG treatment efficacy, as study ARGX-113-1704 showed that reduction total IgG levels and AChR-Ab levels (in AChR-Ab seropositive participants) correlate with reductions in the MG-ADL total score. Clinical efficacy will be measured by the MG-ADL total score and the QMG score, which are well-established measures for assessing disease severity.

The PD of efgartigimod IV at 10 mg/kg and efgartigimod PH20 SC at a fixed dose of 1000 mg will be compared, as per the primary objective of this study (see Section 3). The SC formulation of efgartigimod will include rHuPH20 because the enzyme facilitates the SC delivery of volumes greater than \sim 2 mL and may increase the absorption and dispersion of efgartigimod. rHuPH20 has been approved in the United States as Hylenex recombinant as a permeation enhancer for SC delivery of fluid for achieving hydration and as an adjuvant to increase the dispersion and absorption of other injected drugs. rHuPH20 depolymerizes hyaluronan under physiologic conditions, allowing for a larger volume to be used in rapid SC injections with limited swelling, induration or pain.^{5,6}

The open-label design used in this study will have no impact on the assessment of the PD, PK, and immunogenicity parameters and thus is not expected to impact the primary endpoint and most of the secondary endpoints. Importantly, a double blind study design would be more burdensome for the participants.

4.3. Justification for Dose

The selection of the efgartigimod IV dosage (10 mg/kg q7d) was made based on results from prior clinical studies, including a phase 3 study in participants with gMG (ARGX-113-1704). Administration of efgartigimod IV 10 mg/kg q7d for 4 infusions achieved near-maximal total IgG reduction, resulted in a reduction of pathogenic autoantibodies, and was associated with clinical efficacy in participants with gMG. Furthermore, this dose was well tolerated with no safety concerns in all populations tested thus far.

The efgartigimod PH20 SC dose selected targets a similar total IgG reduction as compared to the efgartigimod IV 10 mg/kg dose, anticipating a similar clinical response. PK/PD modeling indicated that weekly or biweekly doses of efgartigimod PH20 SC 1000 mg result in a comparable effect on IgG levels when compared to efgartigimod IV 10 mg/kg administered q7d or biweekly (q2w).

No safety concerns have been identified to date with SC administration of efgartigimod PH20 SC in the completed phase 1 study ARGX-113-1901 or in ongoing studies in healthy subjects.

4.4. End of Study Definition

The end of the study is defined as the date of the last visit of the last participant in the ARGX-113-2001 study. A participant is considered to have completed the study if he/she completed the EoS visit at day 71 (\pm 3 days), even if the participant did not complete treatment.

5. STUDY POPULATION

Prospective approval of protocol deviations to recruitment and enrollment criteria, also known as protocol waivers or exemptions, is not permitted.

5.1. Inclusion Criteria

Participants are eligible to be included in the study only if **all** of the following criteria apply:

- 1. Must be capable of giving signed informed consent as described in Section 10.1, which includes compliance with the requirements and restrictions listed in the informed consent form (ICF) and in this protocol
- 2. At least 18 years of age at the time of signing the ICF
- 3. Diagnosed with gMG with confirmed documentation and supported by at least 1 of the following:
 - a. History of abnormal neuromuscular transmission demonstrated by single fiber electromyography or repetitive nerve stimulation
 - b. History of positive edrophonium chloride test
 - c. Demonstrated improvement in MG signs upon treatment with oral acetylcholinesterase (AChE) inhibitors as assessed by the treating physician
- 4. Meeting the clinical criteria as defined by the Myasthenia Gravis Foundation of America (MGFA) class II, III, IVa, or IVb
- 5. Abdominal skin tissue allows for absorption and assessment of local safety of the planned SC injection, as determined by the investigator
- 6. An MG-ADL total score of \geq 5 points, with more than 50% of the score due to nonocular symptoms at screening and baseline
- 7. Receiving a stable dose of other gMG treatment (concomitant gMG treatment) prior to screening. For patients receiving nonsteroidal immunosuppressants (NSIDs), steroids, and/or AChE inhibitors as concomitant medications, the following dose conditions apply:
 - a. NSIDs (eg, azathioprine, methotrexate, cyclosporine, tacrolimus, mycophenolate mofetil, and cyclophosphamide): treatment initiated at least 6 months prior to screening and no changes to dose in the 3 months before screening
 - b. Steroids: treatment initiated at least 3 months prior to screening and no dose changes in the month before screening
 - c. AChE inhibitors: stable dose with no dose escalation during the 2 weeks before screening. AChE inhibitors must be withheld for at least 12 hours before the QMG assessment, to be consistent with the revised manual for the QMG test, as recommended by the MFGA
- 8. Contraceptive use should be consistent with local regulations regarding the methods of contraception for those participating in clinical studies and:
 - a. Male participants are eligible to participate if they agree to the following during the intervention period and for at least 90 days after the last study dose of the IMP:
 - Refrain from donating sperm

Clinical Study Protocol ARGX-113-2001 v2.0 Efgartigimod IV and SC

Plus either

- Be abstinent from heterosexual intercourse as their preferred and usual lifestyle (abstinent on a long term and persistent basis) and agree to remain abstinent

Or

 Must agree to use a male condom with a female partner using an additionally highly effective contraceptive method with a failure rate of <1% per year as described in Section 10.5. when having sexual intercourse with a woman of childbearing potential who is not currently pregnant

Or

- Be a sterilized man who has had a documented absence of sperm post-procedure
- b. Female participants are eligible to participate if they are not pregnant or breastfeeding, and they are 1 of the following:
 - Women of nonchildbearing potential (WONCBP), as defined in Section 10.5.1.

Or

- Women of childbearing potential (WOCBP) as defined in Section 10.5.1 and is using a contraceptive method that is highly effective (with a failure rate of <1% per year) during the study intervention and for at least 90 days after the last study dose of the IMP. The investigators should evaluate the potential for contraceptive method failure (eg, noncompliance) in relationship to the first dose of the study intervention
- WOCBP must have a negative highly sensitive serum pregnancy test within the screening period before the first dose of study IMP, see Section 8.2.8.
- Additional requirements for pregnancy testing during and after study intervention are located in Section 8.2.8.
- The investigator is responsible for review of medical history, menstrual history, and recent sexual activity to decrease the risk for inclusion of a woman with an early undetected pregnancy

5.2. Exclusion Criteria

Participants are excluded from the study if **any** of the following criteria apply:

- 1. Are pregnant or lactating, or intend to become pregnant during the study or within 90 days after the last dose of IMP
- 2. Has any of the following medical conditions:
 - a. Clinically significant uncontrolled active or chronic bacterial, viral, or fungal infection at screening
 - b. Any other known autoimmune disease that, in the opinion of the investigator, would interfere with an accurate assessment of clinical symptoms of myasthenia gravis or put the participant at undue risk

Clinical Study Protocol ARGX-113-2001 v2.0 Efgartigimod IV and SC

- c. History of malignancy unless deemed cured by adequate treatment with no evidence of reoccurrence for ≥ 3 years before the first administration of the IMP. Participants with the following cancers can be included at any time:
 - adequately treated basal cell or squamous cell skin cancer
 - carcinoma in situ of the cervix
 - carcinoma in situ of the breast
 - incidental histological findings of prostate cancer (TNM Classification of Malignant Tumors stage T1a or T1b)
- d. Clinical evidence of other significant serious diseases, or the participant has had a recent major surgery, or who have any other condition that, in the opinion of the investigator, could confound the results of the study or put the participant at undue risk
- 3. Worsening muscle weakness secondary to concurrent infections or medications (aminoglycosides, beta-blockers, etc.)
- 4. A documented lack of clinical response to plasma exchange (PLEX)
- 5. Received a live-attenuated vaccine fewer than 28 days before screening. Receiving an inactivated subunit, polysaccharide, or conjugate vaccine any time before screening is not exclusionary
- 6. Received a thymectomy <3 months prior to screening or 1 is planned to be performed during the study period
- 7. The following results from these diagnostic assessments will be considered exclusionary:
 - a. Positive serum test at screening for an active viral infection with any of the following conditions:
 - Hepatitis B virus (HBV) that is indicative of an acute or chronic infection (https://www.cdc.gov/hepatitis/HBV/PDFs/SerologicChartv8.pdf, see Section 10.8)
 - Hepatitis C virus (HCV) based on HCV antibody assay
 - Human immunodeficiency virus (HIV) based on a CD4 count of ≤200 cells/mm³ or test results that are associated with an acquired immunodeficiency syndrome (AIDS)-defining condition, such as: Cytomegalovirus retinitis with loss of vision, *Pneumocystis jiroveci* pneumonia, chronic intestinal cryptosporidiosis, HIV-related encephalopathy, *Mycobacterium tuberculosis* (pulmonary or extrapulmonary), or invasive cervical cancer
 - b. Positive nasopharyngeal swab test for SARS-CoV-2
- 8. Using the following prior or concomitant therapies:
 - a. Use of an investigational product within 3 months or 5 half-lives (whichever is longer) before the first dose of IMP
 - b. Use of any monoclonal antibody within 6 months before the first dose of the IMP

- c. Use of Ig administered intravenously (IVIg), SC (SCIg), or intramuscularly within 4 weeks of screening
- d. Use of PLEX within 4 weeks of screening
- e. Previously participated in a clinical study with efgartigimod and/or products coformulated with rHuPH20 and received at least 1 administration of IMP
- 9. Total IgG levels <6 g/L at screening
- 10. Current or history of (ie, within 12 months of screening) alcohol, drug, or medication abuse
- 11. A known hypersensitivity reaction to efgartigimod, rHuPH20, or any of its excipients

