6.8.3. Prohibited Medication and Procedures

Participants must discontinue from the study intervention if any prohibited therapies are used.

During the study, participants may NOT receive:

- any monoclonal antibody
- other experimental/study IMP
- live or live-attenuated vaccines
- a change in the dose or frequency of their current gMG medication
- a change in concomitant therapy for gMG
- PLEX, IVIg, immunoadsorption, or a change in dosage or type of corticosteroid used as a monotherapy or in combination

PLEX, Ig therapy (IVIg and SCIg), immunoadsorption, or a change in dosage or type of corticosteroid are considered rescue therapy if both of the following conditions apply:

- 1. The treating physician believes that the participant's health is in jeopardy if rescue therapy is not provided, and
- 2. The participant is deteriorating clinically according to the protocol-defined criteria, which includes at least 1 of the following:
 - a. new or worsening of respiratory/bulbar symptoms, or
 - b. at least a 2-point increase in any individual nonocular items on the MG-ADL scale as compared to the previous visit

The date and time of rescue medication administration, as well as the name, dosage regimen, and response to the rescue medication will be recorded in the eCRF.

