9.4.1. General Considerations

- The baseline value will be defined as the last assessment prior to the first administration of efgartigimod.
- All study visits will be recalculated based on actual dates and will be referred to as "analysis visits," which will be used in the statistical analyses. The rules for calculating the analysis visits will be documented in the SAP. Rules for inputting partial dates or missing dates will also be documented in the SAP.

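### Exclusion criterion 8 has a 4-week washout for Ig therapy and PLEX but none for immunoadsorption, which section 6.8.3 lists beside them; the 6 g/L IgG floor closes the gap only in part

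*Protocol*

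**What the plan says.** **Before entry (Protocol 5.2).** Criterion 8c excludes "Use of Ig administered intravenously (IVIg), SC (SCIg), or intramuscularly within 4 weeks of screening". Criterion 8d excludes "Use of PLEX within 4 weeks of screening". No eligibility criterion in 5.1 or 5.2 names immunoadsorption.

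**On study (Protocol 6.8.3).** The prohibited list includes "PLEX, IVIg, immunoadsorption, or a change in dosage or type of corticosteroid used as a monotherapy or in combination". The next paragraph states that "PLEX, Ig therapy (IVIg and SCIg), immunoadsorption, or a change in dosage or type of corticosteroid are considered rescue therapy" when two clinical conditions are met. Immunoadsorption is therefore a separate item from PLEX in both places.

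**Other criteria that bear on such a patient.**
- Criterion 9 excludes "Total IgG levels <6 g/L at screening".
- Criterion 2d lets the investigator exclude for any other condition that "could confound the results of the study or put the participant at undue risk".
- Inclusion 7 requires "Receiving a stable dose of other gMG treatment (concomitant gMG treatment) prior to screening". Its time windows cover only nonsteroidal immunosuppressants, steroids and AChE inhibitors.

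**Endpoint.** The primary variable is the percent reduction in total IgG from baseline at day 29 (9.4.2). Section 9.4.1 says: "The baseline value will be defined as the last assessment prior to the first administration of efgartigimod". The primary ANCOVA has treatment as factor and baseline IgG as covariate.

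**The concern.** Immunoadsorption removes IgG, and total IgG is the primary variable. The protocol treats the procedure like PLEX once the patient is enrolled, but not in the weeks before. Because 6.8.3 lists the two separately, PLEX in 8d cannot safely be read to include immunoadsorption.

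A patient treated shortly before screening could then start from a day 1 value that is low and rising back to its usual level. Percent reduction from that value is too small whichever product is given. At stake are a few outlying values in a comparison planned on an SD of 7.5 to 10 with a margin of 10. The same depleted starting point would enter the IgG subtype, AChR-Ab and AUEC endpoints.

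**Working it through.** **1. The plan's own figures.** From 9.2: margin 10, true difference 2, one-sided 2.5%, two-sample t-test. Power is the probability that a noncentral t with 2n − 2 degrees of freedom and noncentrality (10 − 2)/(SD × √(2/n)) exceeds its critical value.

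| SD | n per arm for 90% power | Stated | Power at stated n |
|---|---|---|---|
| 7.5 | 20 | 20 | 90.8% |
| 8.5 | 25 | 25 (50 in total) | 90.3% |
| 10 | 34 | 34 (68 in total) | 90.2% |

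The stated figures reproduce. With 55 per arm (110 randomized 1:1), power is 99.98% at SD 7.5 and 98.6% at SD 10. The eligibility wording affects none of these.

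**2. Size for one patient.** The protocol gives no turnover values, so these are assumptions: natural IgG half-life 14, 21 or 28 days; usual IgG (SS) 10, 12 or 14 g/L; fraction left after the procedure 30, 40 or 50%; procedure 3, 7 or 14 days before screening; day 1 a further 7 or 14 days later. That makes 162 combinations.

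- Recovery: IgG(t) = SS × (1 − (1 − fraction left) × e^(−kt)), with k = ln 2 / half-life.
- On drug, elimination is multiplied by r: IgG at day 29 = SS/r + (baseline − SS/r) × e^(−28rk).
- r is set so that an undepleted patient shows the 62.2% reduction given in 9.2: r = 2.75, 2.98 and 3.27 for the three half-lives.

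Central case (21 days, 12 g/L, 40% left, 7 days to screening, 7 more to day 1; k = 0.0330):
- Screening: 12 × (1 − 0.6 × 0.794) = 6.3 g/L, which passes criterion 9.
- Baseline: 12 × (1 − 0.6 × 0.630) = 7.46 g/L.
- Day 29: 4.03 + (7.46 − 4.03) × 0.0637 = 4.25 g/L.
- Reduction: 1 − 4.25/7.46 = 43.1%, against 62.2%. The shortfall is 19.1 points, or 19.1/7.5 = 2.5 SD.

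Over the grid, criterion 9 removes 64 of 162 cases. The 98 that pass show 37.4 to 57.1%, a shortfall of 5.1 to 24.8 points. One such patient moves a 55-patient arm mean by 5.1/55 = 0.09 to 24.8/55 = 0.45 points.

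**3. Size for the trial.** Simulation of the baseline-adjusted ANCOVA: 55 per arm, SD 7.5, 3,000 runs. Assumed: usual IgG about 11 g/L (SD 2.5), affected baselines at 60% of usual but not below 6 g/L, day 29 level unaffected by the earlier removal, and the number of affected patients.

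| Affected IV / SC | Estimate, true difference 2 | Power | Estimate, true difference 10 | Type I error |
|---|---|---|---|---|
| 0 / 0 | 1.98 | 100% | 10.01 | 1.8% |
| 1 / 1 | 1.97 | 99.9% | 10.10 | 1.4% |
| 3 / 3 | 2.07 | 99.6% | 10.34 | 0.9% |
| 6 / 6 | 2.06 | 99.1% | 10.62 | 0.2% |
| 3 / 0 | 0.90 | 100% | 8.87 | 8.0% |
| 0 / 3 | 3.21 | 99.0% | 11.40 | 0.2% |
| 6 / 0 | −0.14 | 100% | 7.86 | 18.8% |

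The Monte Carlo error near the nominal 2.5% is √(0.025 × 0.975/3000), about 0.3 points, so small differences between rows mean little. Balanced contamination is conservative. Only an excess in the IV arm raises the type I error.

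**The case against.** A reader might infer that any patient whose IgG has just been removed is eligible, and that the primary comparison is therefore distorted. The documents support neither.

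- **Criterion 9 removes the deepest depletion.** In the grid it excludes 36 of the 54 cases treated 3 days before screening and 38 of the 54 with usual IgG of 10 g/L. The central patient treated 3 days before screening would have 5.5 g/L and be excluded; at 7 days the same patient passes only narrowly.
- **Other safeguards exist.** Criterion 2d allows discretionary exclusion. Inclusion 7 opens with a general stability requirement, and 6.8.2 lists only three classes as permitted gMG therapy. Prior gMG procedures are recorded for a year back (6.8.1), and the sponsor or CRO confirms eligibility (section 8).
- **The analysis is fairly robust.** Central randomization makes the effect non-differential in expectation.
- **The washout is not a complete cure.** With the procedure 28 days before screening, the central patient still shows 54.9%, a shortfall of 7.3 points. The gain there is about 12 points (19.1 − 7.3), not 19.

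These points stand and limit the severity. They do not remove the inconsistency. A fixed IgG floor is not a washout: a patient usually at 12 g/L can be halved and still pass. Discretion and a stability clause without a time window are weaker than the explicit rule given for PLEX. The ANCOVA covariate cannot tell a transiently low baseline from a stable low one, and the simulated shifts remain with that covariate in the model.

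**Conclusion.** The omission is real and conflicts with the protocol's own grouping in 6.8.3. A patient with recent immunoadsorption and screening IgG of 6 g/L or more meets the written criteria. That patient's percent reduction is understated by about 5 to 25 points, on turnover values that are assumed throughout.

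The trial-level effect is probably small. The documents give no frequency of prior immunoadsorption, and few patients are likely to be affected. With up to 6 affected in each arm, the estimate moves by about 0.1 at a true difference of 2, power stays at 99% or more, and the test becomes conservative. Harm to the noninferiority conclusion needs a chance imbalance towards the IV arm: with 3 against 0, about 1.1 points and a type I error near 8%. It would be wrong to infer that the primary result is unreliable or the trial underpowered. The severity is minor.

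**What to change.** Reconcile criterion 8 with 6.8.3. The simplest way is to extend 8d to immunoadsorption on the terms already set for PLEX: *Use of PLEX or immunoadsorption within 4 weeks of screening*. If the different treatment before entry is intended, the protocol should say why.

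The cost is one phrase in the next amendment and in the eligibility checklist. No new data are needed: the procedure records required by 6.8.1 let sites apply the rule and let the sponsor check patients already enrolled. A few patients would wait up to 4 weeks before screening, as PLEX patients already do. Some depletion would remain after 4 weeks (about 7 points in the central case), a residual the protocol already accepts for PLEX.
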